#### 4.3.1.2 Data Handling

All output will be incorporated into Microsoft Excel or Word files, sorted and labeled according to the International Conference on Harmonization (ICH) recommendations, and formatted to the appropriate page size(s).

Tabulations will be produced by randomized treatment group and overall, unless otherwise specified.

Categorical variables will be tabulated with counts and percentages. Continuous variables will be summarized with univariate statistics (e.g., n, mean, standard deviation (SD), median, minimum, and maximum). The minimum and maximum will be presented with the same precision as the data, the mean and percentiles will be presented with the precision of the data + 1 decimal place, and the SD will be presented with the precision of the data + 2 decimal places.

Unless otherwise specified, all statistical tests will be 2-sided with alpha = 0.05. Tests will be declared statistically significant if the calculated p-value is  $\leq 0.05$ . P-values < 0.0001 will be presented as "<0.0001". Otherwise, p-values will be presented to 4 decimal places.

Change from baseline is calculated by subtracting the baseline value from the observed postbaseline value at any subsequent visit. Baseline (specific to the randomized phase or to the open-label phase) will be defined as last available assessment on or before the 1st day the participant receives study medication for that phase. Tabulations of the following endpoints will present the number of unique participants with an event: protocol deviations; non-study medications; AEs; and laboratory abnormalities. Thus, for these endpoints, multiple occurrences of the same event are counted only once per participant.

Unique Participant ID's will take the form "BHV4157-203-site#-participant#". By-participant listings will display unique PID and "(Age/Sex/Race)" stacked together in the same column using the following conventions:

- Age at informed consent will be displayed truncated to an integer
- Sex will be displayed abbreviated as "F" for female and "M" for male
- Race will be abbreviated as "A" for Asian", "B" for Black or African American, "I" for American Indian or Alaska Native, "M" for multiple, "N" for Native Hawaiian or Other Pacific Islander, and "W" for White

A footnote will describe race abbreviations, e.g., "Race: A = Asian, B = Black or African American, I = American Indian or Alaska Native, M = Multiple, N = Native Hawaiian or Other Pacific Islander, W = White". Participants who report more than one race will be counted only once in the "Multiple" category. Missing age, sex, or race will be displayed as a single blank space.

Note that "(Age/Sex/Race)" will not be displayed in listings of randomization scheme and codes, batch numbers, and demographics.

#### 4.3.2 Computing Environment

All statistical analyses will be performed using SAS statistical software (Version 9.4) or R (Version 4.0.0), as specified. Medical history and AEs will be coded using the Medical Dictionary for Regulatory Activities (MedDRA, Version 23.) Concomitant medications will be coded with WHO Drug (Global March 2019) using the WHODrug Insight tool. Laboratory abnormalities will be classified as clinically significant if they are coded as Grade 3 or 4 according to the numeric laboratory test criteria in Common Technical Criteria for Adverse Events (CTCAE) Version 5.0 (2017). For laboratory tests not included in CTCAE Version 5.0, abnormalities will be coded according to Division of AIDS (DAIDS) Table for Grading the Severity of Adult and Pediatric Adverse Events Corrected Version 2.1 (2017).

#### 4.3.3 Adjustments for Covariates and Stratification

The analysis of the primary endpoints and other efficacy endpoints will be analyzed by comparing the change in efficacy outcome at week 48 between treatment groups using a mixed model with repeated measures (MMRM). Fixed effects in the model are APOE status (e4 carrier vs e4 noncarrier), MMSE (mild vs moderate) status, site, baseline value of the endpoint, treatment group (active vs. placebo), visit, visit x baseline and visit x treatment group interaction. Visit is treated as a categorical variable (see section 4.2.8 for definition of visit windows to be use). Subject will be included as random effects in the model. Sites with only one subject will be pooled together.

A stratified permuted block randomization procedure will be used. The stratification factors will be Screening Visit MMSE [mild: 20 to 24; moderate: 14 to 19] and Site.

#### 4.3.4 Multiple Comparisons/Multiplicity

Type 1 errors will be controlled for the co-primary and multiple secondary efficacy endpoints by testing these endpoints with a gate-keeping procedure at a family wise two-sided alpha level of 0.05. The co-primary endpoints, ADAS-Cog 11 and CDR-SOB, will be tested, first testing the ADAS-cog and then, if significant, testing the CDR-SOB. The primary objective of the trial is met only when both co-primary endpoints are significant. If the co-primary endpoints are significant, then the key secondary efficacy endpoints will be tested using the Holm-Bonferroni step down procedure, at family-wise significance level 5%.

If the tests of the primary endpoints are not significant, then the adjusted and unadjusted pvalues for the secondary endpoints will be presented only for descriptive purposes, and no conclusions will be drawn from these results.

No attempt will be made to adjust for multiplicity when testing the exploratory endpoints. Any exploratory endpoints subjected to significance testing are evaluated at an unadjusted two-sided alpha level of 0.05 and are presented for descriptive purposes only.

#### 4.3.5 Subpopulations

The subgroups of interest for this study are:

- Sex
- APOE (e4 vs no or missing)
- Mild vs moderate (mild AD:MMSE 20 to 24; moderate AD: MMSE 14 to 19)
- Participation during Covid-19 (opportunity to complete randomization phase before March 13, 2020 vs on or after March 13, 2020)

Except where indicated otherwise, descriptive summaries will be provided for the co-primary endpoints for each subgroup.

#### 4.3.6 Withdrawals, Dropouts, and Loss to Follow-up

Participants who withdraw from the study will not be replaced.

#### 4.3.7 Missing, Unused, and Spurious Data

Unless otherwise noted, efficacy analyses will be based on observed data only. No missing data will be imputed. Imputation will be done for sensitivity analyses only.

For efficacy analyses, partial or missing dates will not be imputed. The relative study days, where determined, will be calculated for full dates only.

If the start date/time of an AE is partially or completely missing, the date/time will be compared as far as possible with the date/time of the start of administration of study drug. The AE will be assumed to be treatment-emergent if it cannot be definitively shown that the AE did not occur or worsen during the treatment-emergent period (worst-case approach).

The following general rules will be used:

- If the start time of an AE is missing but the start date is complete, an AE will only be excluded as being treatment-emergent if the start date is before the date of study drug administration or if the stop date/time is before study drug administration.
- If the start time and day are missing but the start month and year are complete, an AE will only be excluded as being treatment-emergent if the start month/year is before the month/year of study drug administration or if the stop date/time is before study drug administration.
- If the start day and month are missing but the start year is complete, an AE will only be excluded as being treatment-emergent if start year is before the year of study drug administration or if the stop date/time is before study drug administration.
- If the start date is completely missing, an AE will be considered treatment-emergent unless the stop date/time is before study drug administration.

#### 4.3.8 Visit Windows

The protocol-specified in-clinic visit windows are  $\pm$  7 days during the Randomization Phase, however, analysis windows will be continuous to include all data. Refer to Appendix 1 for details on the expected evaluation intervals for the details on the schedule of assessments during the Randomization and Extension Phases. The data portal contains a report where all visits and their acceptable windows will be projected at the baseline visit. The baseline visit for the randomization phase is expected to be the date of randomization and first dose of randomized treatment.

#### **On-Treatment Analysis Windows**

# Table 1:Analysis Windows for Efficacy Parameters: ADAS-cog and CDR in
the 48 week Randomization Phase

Evaluation	Protocol-Specified Day	Analysis-Specified Interval
Randomization Phase		
Week 12	Day 84	Day 2-126
Week 24	Day 168	Day 127-210
Week 36	Day 252	Day 211-294
Week 48	Day 336	Day 295-420

Note: Baseline assessment will be defined as the last available assessment on or before first day of randomization phase study drug [For CDR the window for baseline assessment will be extended to include assessments up to and including Day 2 of study drug as one subject completed the CDR after starting study treatment. This assessment was felt to still be a valid baseline assessment due to the limited treatment at the time of assessment. The Week 12 window will be adjusted accordingly to Day 3-126.]. Days based on days from first day of randomization phase study drug.

# Table 2:Analysis Windows for All Other Efficacy Parameters Including NPI,
ADCS-ADL, MMSE, MoCA, Volumetric MRI, CSF Biomarkers and
Blood Biomarkers and NACC measures in the 48 week
Randomization Phase.

Evaluation	Protocol-Specified Day	Analysis-Specified Interval
Randomization Phase		
Week 24	Day 168	Day 2-252
Week 48	Day 336	Day 253-420

Note: Baseline assessment will be defined as the last available assessment on or before first day of randomization phase study drug. Days based on days from first day of randomization phase study drug.

Table 3:	Analysis Windows for Safety Parameters: Sheehan Suicidal
	Tracking, Vital Signs, Lab Assessments, PK and ECG

Evaluation	Protocol-Specified Day	Analysis-Specified Interval
Randomization Phase		
Week 4	Day 28	Day 2-42
Week 8	Day 56	Day 43-70
Week 12	Day 84	Day 71-98
Week 16	Day 112	Day 99-126
Week 20	Day 140	Day 127-154
Week 24	Day 168	Day 155-182
Week 28	Day 196	Day 183-210
Week 32	Day 224	Day 211-238
Week 36	Day 252	Day 239-266
Week 40	Day 280	Day 267-294
Week 44	Day 308	Day 295-322
Week 48	Day 336	Day 323-420

Note: Baseline assessment will be defined as the last available assessment on or before first day of randomization phase study drug. Days based on days from first day of randomization phase study drug.

If a participant has more than one record within an analysis window, the latest record within the window will be used in the analysis.

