8.1.7 Week 24 (+ 7 days)

All participants returning for week 24 will undergo the following procedures:

- Physical exam
- Vital signs (sitting blood pressure, pulse, temperature, respiration rate)
- Weight
- Documentation of concomitant treatment
- Documentation of adverse events
- Blood samples for:
 - Safety laboratory tests (hematology and serum chemistry, as listed in Section 8.2)
 - Pharmacokinetics (in plasma)
 - o Biomarker/bio banking
- Urinalysis (see Section 8.2)
- Resting 12-lead ECG
- Lumbar puncture* (± 14 days of week 24)
- Sheehan Suicidality Tracking Scale
- ADAS-Cog 11
- CDR-SOB
- Volumetric MRI (± 14 days of week 24)
- NPI
- ADCS-ADL
- MMSE
- MoCA
- Research Satisfaction Survey

At this visit, participants will receive a supply of study drug with instructions on how to take it. Participants will be given an appointment to return in 12 weeks (± 7 days).

*NOTE: Participants who have consented to participate in the CSF sub-study will undergo a lumbar puncture for CSF within 14 days prior to this visit. Plasma samples for PK for this subset of participants should be drawn at the time of lumbar puncture. The participant's vitals should be assessed before and after the procedure, or per standard local practice. INR, PT, PTT and platelets should be assessed at the site's local laboratory at least 24 hours, and within normal range, prior to the lumbar puncture. The lumbar puncture should be done after the MRI scan if performed on the same day. If the lumbar puncture is performed on a separate day from the MRI and occurs before the MRI, then there must be at least a 3-day window between the lumbar puncture and the MRI. If the lumbar puncture is performed on a separate day from the MRI and occurs after the MRI, then there is no window (waiting period) between the MRI and lumbar puncture. If a participant in the CSF sub-study is terminating early, they do not need to undergo this lumbar puncture. However, every effort will be made to encourage the participant's ongoing voluntary

participation and to explain that CSF collection may provide informative information in the future for the field of AD.

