8.3 Pharmacokinetic Assessments

A plasma sample for pharmacokinetic (PK) should be collected at baseline, week 4, week 8, week 12, week 24, and week 48 of the double-blind phase of the trial. Participants should take their dose at their routine time on the days of these visits. Date and time of last dose should be collected in case report forms for entry into the EDC system. Participants who are able to be scheduled for a morning visit should be instructed to hold their dose of study drug that morning until after a PK trough sample is obtained, if possible and appropriate in the judgment of the investigator.

PK samples should be drawn if there are any SAEs that could possibly be drug-related or severe AEs that could be drug-related.

In addition, for participants undergoing lumbar puncture, plasma samples for PK should be drawn at the time of lumbar puncture for Week 24 and Week 48 visits for the double blind placebo phase. Date and time of last dose should be collected in case report forms for entry into the EDC system.

There is no PK sampling during the OLE phase.

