 - Week 24 and week 48 vMRI: the protocol window for vMRI at week 24 and week 48 is 14 days before and up to 14 days after the clinic visit. If participant is terminating early at 36 week or after, obtain vMRI if MRI is performed on the same day as a lumbar puncture at week 48, the vMRI must be conducted before the lumbar puncture. Otherwise, at least a 3-day window between vMRI and the lumbar puncture is required.
- 12 It is anticipated that lumbar puncture will be performed on an estimated 100 study participants as part of a sub-study (separate informed consent required).
- Only for the CSF sub-study. Visit windows for CSF are: up to 14 days prior to first dose of study medication and up to 14 days prior to weeks 24 and 48. If a participant in the CSF sub-study is terminating early, they do not need to undergo lumbar puncture.
- Post lumbar puncture safety follow up telephone call must occur 1 to 3 days after the lumbar puncture is performed.
- First dose of study medication will be given in the clinic at the baseline clinic visit after completion of the baseline visit procedures.
- Participants will receive a phone call during Week 2 from site study personnel in order to assess study drug tolerability. If tolerable, then the participant will be instructed to proceed with dose escalation.
- 17 Treatment blinding questionnaire to be administered to site PI and Raters.

Table 3: Schedule of Assessments and Events – Open-Label Extension Phase

Visit Number	1	2	3	4	5	6	7	8	9	10	
Study Visit Timepoint	Baselinel	Abbrev- iated Drug Dispensat ion Visit ²	Ext Week 2 (+/- 7 days)	Ext Week 4 (+/- 7 days)	Ext Week 8 ³ (+/- 7 days)	Ext Week 12 (+/- 7 days)	Ext Week 24 (+/- 7 days)	Ext Week 36 (+/- 7 days)	Ext Week 48 or Early Term (+/- 7 days)	Week2 Post last dose (+/- 7 days)	Unsched- uled Visit ⁴ (+/- 7 days)
Informed Consent	X	X									
Medical History	X										
Adverse Event Assessment	X	X	X	X	X^3	X	X	X	X	X	X
Telephone Check-in ⁵ Includes AE assessment and concomitant medication review			X		X ³						
Laboratory Assessments ⁶	X			X	X^3	X	X	X	X		
Urinalysis	X						X		X		
Physical Exam	X								X		
Physical Measurement - Weight	X						X		X		
Vital Signs	X	X		X		X	X	X	X	X	X
12-Lead ECG	X					X	X		X		
Concomitant Medication Review	X	X	X	X	X	X	X	X	X	X	X
Sheehan Suicidality Tracking Scale (S-STS)	X	X		X		X	X	X	X	X	
Dispense Study Drug	X	X		X		X	X	X			
Volumetric MRI ⁷	X								X		
ADAS-Cog 11	X						X		X		
CDR-SOB	X						X		X		

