#### 4.9 Pharmacokinetic Evaluations

All PK analyses will be conducted using the treated population.

A PK sample will be collected at baseline, weeks 4, 8, 12, 24 and 48 of the Randomization Phase. Additionally, PK samples should be drawn if there are any SAEs that could possibly be drug related or severe AEs that could be drug related. Date and time of doses on the day of visits and day prior will be collected in the case report forms along with the time of last meal.

Participants who are able to schedule a morning visit for baseline, weeks 2, 4, 8, 12, 24 and 48 can be instructed to hold their dose of study drug that morning until after a PK trough sample is obtained, if possible and appropriate.

Individual concentrations will be summarized by visit for the Randomization Phase. Plasma concentrations below the limit of quantification (BQL) will be considered to be 0 concentration. Missing values will not be imputed.

Individual plasma concentration data will be displayed in listings for the Randomization Phase.

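### SAP Table 3 sorts PK samples into 4-weekly day windows, so event-triggered and lumbar-puncture samples can displace scheduled values or appear under weeks with no planned PK draw

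*SAP*

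**What the plan says.** SAP 4.3.8 gives the day windows. It states that "analysis windows will be continuous to include all data". Table 3, whose title includes "Tracking, Vital Signs, Lab Assessments, PK and ECG", has twelve rows from Week 4 to Week 48 at 4-week steps, and the rule beneath it is: "If a participant has more than one record within an analysis window, the latest record within the window will be used in the analysis". CSF biomarkers are in Table 2 instead, which has only two windows: Week 24 (Day 2–252) and Week 48 (Day 253–420).

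Protocol 8.3 and SAP 4.9 schedule PK at baseline and Weeks 4, 8, 12, 24 and 48. There are two further sources of PK plasma:

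- Lumbar puncture. Protocol 8.3 says that "plasma samples for PK should be drawn at the time of lumbar puncture for Week 24 and Week 48 visits" and presents these as additional samples. The notes in Protocol 8.1.7 and 8.1.9 say that sub-study participants "will undergo a lumbar puncture for CSF within 14 days prior to this visit". The Appendix I footnote on CSF has "up to 14 days prior to weeks 24 and 48". The procedure lists in 8.1.7 and 8.1.9 instead give ±14 days.
- Events. SAP 4.9: "Additionally, PK samples should be drawn if there are any SAEs that could possibly be drug related"; severe AEs that could be drug related are covered as well.

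SAP 4.9 then summarizes concentrations by visit and lists individual values. It has no rule for the lumbar-puncture or event-triggered samples.

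**The concern.** Seven of the twelve Table 3 windows (Weeks 16, 20, 28, 32, 36, 40 and 44) have no planned PK draw, so anything that falls there is an unscheduled or displaced sample shown as a visit. In the five windows that do have a planned draw, the latest-record rule does not distinguish a scheduled sample from one taken because of an adverse event. A level drawn because something went wrong is a selected value and may differ in dose and time since dose. In the by-visit table it would stand in for the planned value without any mark.

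The lumbar-puncture plasma is the drug level taken with the CSF. Under Tables 2 and 3 the two samples from one procedure can carry different week labels without any protocol deviation. At stake is whether the only PK summary in SAP 4.9 shows what its visit labels say.

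**Working it through.** **Inputs.** From SAP Table 3: Week 20 = Day 127–154, Week 24 = Day 155–182, Week 28 = Day 183–210, Week 44 = Day 295–322, Week 48 = Day 323–420. From SAP Table 2 (CSF): Week 24 = Day 2–252, Week 48 = Day 253–420. Clinic visits have ±7 days (SAP 4.3.8). Lumbar-puncture timing is as in Protocol 8.1.7, 8.1.9 and Appendix I.

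**1. Reproduce Table 3.** Window for week w = Day (7w − 13) to Day (7w + 14). Week 20: 140 − 13 = 127 to 140 + 14 = 154. Week 44: 308 − 13 = 295 to 308 + 14 = 322. Every row matches except the start of Week 4 (printed as Day 2; the rule gives Day 15) and the end of Week 48 (printed as Day 420; the rule gives Day 350).

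**2. Scheduled clinic samples.** Visits at ±7 days fall on Days 21–35, 49–63, 77–91, 161–175 and 329–343. The windows are Days 2–42, 43–70, 71–98, 155–182 and 323–420. All visits fall inside, and still do if each is counted one day later.

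**3. Event-triggered samples.** The five windows with a scheduled draw cover 41 + 28 + 28 + 28 + 98 = 223 of the 419 days from Day 2 to Day 420. The other seven cover 7 × 28 = 196.
- Week 4 visit on Day 28, event sample on Day 38: both are in Day 2–42, the later one is used, and the scheduled value drops out.
- Event sample on Day 20, visit on Day 28: the visit sample is used and the event sample drops out.
- Event sample on Day 110: it lies in Day 99–126 and becomes a Week 16 PK value.

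**4. Lumbar-puncture samples.** Let u be the visit's deviation from target (−7 to 7) and v the days from puncture to visit (0 to 14). The plasma is labelled Week 20 when 168 + u − v ≤ 154, that is v ≥ 14 + u. For u = −7, −6, …, 0 this gives 8 + 7 + … + 1 = 36 of 15 × 15 = 225 pairs. Week 48 has the same algebra (336 + u − v ≤ 322). Table 3 prints the targets as Days 168 and 336. If the first dosing day is Day 1, exactly 24 or 48 weeks later is Day 169 or 337, and the count becomes 7 + 6 + … + 1 = 28.

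| Reading of the puncture window | Target Day 168/336 | Target Day 169/337 |
|---|---|---|
| Up to 14 days before the target | 1/15 (7%) | 0/15 |
| Up to 14 days before a visit within ±7 days | 36/225 (16%) | 28/225 (12%) |
| ±14 days of such a visit, Week 24 | (36 + 28)/435 (15%) | (28 + 36)/435 (15%) |
| ±14 days of such a visit, Week 48 | 36/435 (8%) | 28/435 (6%) |

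In the Week 24 row for ±14 days, the second term counts late punctures labelled Week 28. Week 48 has no such spill because its window runs to Day 420. In every case the CSF is labelled Week 24 or Week 48 by Table 2.

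Example: visit on Day 163 (u = −5) and puncture on Day 151 (v = 12). Plasma is Week 20 and CSF is Week 24.

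**5. Latest-record rule within the right window.** A puncture sample on Day 160 followed by a clinic sample on Day 168 is dropped from the Week 24 summary. Under the ±14-day wording, a puncture on Day 175 after a Day 168 visit would instead replace the clinic sample.

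**The case against.** The strongest reply is that little depends on these labels. PK is exploratory, SAP 4.9 plans only by-visit summaries and listings, and the CSF model in SAP 4.8.5.4 has no drug-level term. A reader might infer that Table 3 breaks the link between plasma and CSF. The documents do not support that: no paired analysis is planned, dose dates and times around the puncture go into the CRF (Protocol 8.8), and a window label deletes nothing. This stands and limits the point to the summary table.

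Second, where the clinic sample is also drawn, and later, it is the one used for Week 24 or 48 whatever label the earlier puncture sample carries. This also stands, on the reading that puncture samples are additional (Protocol 8.3). If the notes in 8.1.7 and 8.1.9 mean that the puncture sample replaces the visit sample, an early puncture leaves that participant with no Week 24 or Week 48 PK value.

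Third, continuous windows that keep all data are a deliberate choice, and Day 151 is nearer to Day 140 (11 days) than to Day 168 (17 days). That is fair for a sample with no intended visit. It is less so for one that the protocol ties to Week 24.

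Fourth, a reader might take every SAE-triggered sample to count as a scheduled visit. It does so only in five windows, and there only when it is the latest record.

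**Conclusion.** The point holds as a gap in the labelling rules, with small consequences. As written, an event-triggered sample can replace a scheduled PK value or create an unplanned PK week, and plasma from an allowed lumbar puncture can carry a different week from its CSF.

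Under the wording that places the puncture up to 14 days beforehand, the mismatch covers 0–7% of allowed days when tied to the target and 12–16% of allowed day pairs when tied to a visit within ±7 days. The ±14-day wording around the visit gives 15% at Week 24 and 6–8% at Week 48. These shares weight all allowed days equally. The documents give no distribution of actual visit or puncture days, so none of them is a forecast.

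It is tempting to turn 16% of the estimated 50 active CSF participants into 0.16 × 50 = 8 mislabelled samples per time point. That also assumes that all 50 have each puncture, but early terminators need not, and Protocol 8.8 makes the sentinel cohort's Week 48 sample optional.

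How often events would prompt a PK draw cannot be derived from the documents. Scheduled clinic samples within ±7 days are labelled correctly, and no efficacy or safety conclusion is shown to depend on this.

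**What to change.** In SAP 4.9, with PK taken out of the Table 3 title:

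1. Summarize by visit only the scheduled clinic PK samples, in day windows built around the scheduled PK weeks. Midpoints between Days 28, 56, 84, 168 and 336 give cut-points at Days 42, 70, 126 and 252, in line with those already in Tables 1 to 3. Assign early-termination samples by actual study day (Day 60 would be Week 8). Do not move PK to the nominal CRF visit: Visit 9 serves as both Week 48 and early termination, so such a sample could be labelled Week 48.
2. Give each lumbar-puncture PK sample the Week 24 or Week 48 label of its paired CSF sample, and report it separately from the clinic samples.
3. List PK samples triggered by an SAE or severe AE with the event, the dose and the time since dose, outside the by-visit summary and the latest-record rule.

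The two wordings of the lumbar-puncture window in Protocol 8.1.7 and 8.1.9 (±14 days in the procedure lists, within the 14 days before in the notes) must be reconciled. So must the statements on whether the puncture sample adds to the visit sample or replaces it.

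The analysis changes cost SAP wording and programming only, and the reconciliation is a protocol clarification. No new data are needed.
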